NCT02862210

Low-dose lithium for the treatment of behavioral symptoms in Frontotemporal Dementia Standard Operating Procedures Manual Version date 31May2021

Introduction

The Alzheimer's Drug Discovery Foundation funded a study titled "Low-dose lithium for the treatment of behavioral symptoms in Frontotemporal Dementia," which examines the efficacy and side effects of low dose lithium treatment for agitation/aggression/repetitive behaviors in 60 patients with FTD in a randomized, double blind, placebo-controlled 12-week trial.

Lithium carbonate or placebo will be started at an oral dose of 150 mg daily, with subsequent dose titration to 300mg/day at the 2-week visit, 450mg/day at the 4-week visit, and 600mg/day (maximum daily dose) at the 6-week visit. This upward dose titration will occur if clinically indicated, tolerated by the patient, and based on real/sham lithium blood level. An absence of response at lower doses without intolerable side effects is defined as clinically indicated. Assessments will take place at study entry (0 weeks), 2, 4, 6, 8, and 12 weeks, and the time-point of protocol exit for dropouts. Lithium levels will be drawn approximately 12-14 hours after the last dose.

Our primary outcome measures will be the Neuropsychiatric Inventory and the Clinical Global Impression scales.

Optimal target serum levels of lithium will be between 0.2 to 0.6 mmol/L due the risk of dropout due to lithium toxicity at higher levels. Clinical response of symptoms and side effects experienced by the patient will be primary in guiding oral lithium dose adjustment, and will override the information obtained from serum lithium levels if such a choice needs to be made.

This study will provide useful data on the efficacy and side effects of low-dose lithium treatment for FTD patients with symptoms of agitation/aggression, and possibly for other behavioral symptoms such as aberrant motor behaviors. The potential utility of lithium would provide an alternative for patients who show no/minimal response to or experience intolerable side effects while on antidepressants and antipsychotics.

During COVID, it was decided that the protocol would be updated to allow for a portion of the study visits to occur remotely. This was largely to reduce risks to participants once the study reopened (I.e. to minimize time traveling to a hospital), but also, we hoped this would make the study less burdensome to patients and study partners moving forward.

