- Schedule visit with participant for 2 weeks after they receive the study drug kit. During this call, also confirm dosing schedule (1 pill in evenings) and ask them to use the same bottle during the 2 week period.
- □ Create zoom link & send along with date/time of visit & visit schedule to the study partner
- Send a calendar invitation to the study physician. In the calendar invitation, include:
 - o Zoom link
 - Links to clinician forms within REDCap for the correct subject/week
 - o List of clinician forms: Treatment emergent symptoms, CGI-Severity, CGI-Change
 - Current subject medication dose, anticipated dose change after visit, & any other relevant information

During visit:

- □ Complete medication compliance check: have study partner count pills remaining in the bottle they have been using. Each bottle contains 28 pills, so calculate the number of pills that should be remaining (14 if 2 weeks from kit receipt)
- On REDCap, complete the following forms with the study partner:
 - Visit registry, concomitant meds, NPI, Stereotypic/Ritualistic behaviors, study drug issue/return log

Post-visit:

- □ If no contradictions per study clinician, instruct participant/study partner to increase dose to 300mg/day (one pill mornings, one pill evenings), using a new bottle.
- □ Schedule Week 4 visit with participant for 2 weeks after their week 2 visit.
- Obtain clinician signature on REDCap study drug issue/return log, resolve any missing data from clinician forms

Week 4

Pre-visit:

- □ Create zoom link & send along with date/time of visit & visit schedule to the study partner
- Send a calendar invitation to the study physician. In the calendar invitation, include:
 - o Zoom link
 - o Links to clinician forms within REDCap for the correct subject/week
 - List of clinician forms: Treatment emergent symptoms, CGI-Severity, CGI-Change, Simpson-Angus, Lawton, CDR
 - Current subject medication dose, anticipated dose change after visit, & any other relevant information

During visit:

- □ Complete medication compliance check: have study partner count pills remaining in the bottle they have been using. There should be 0 remaining if 14 days have passed since the previous visit (and they were taking 2 pills daily).
- □ On REDCap, complete the following forms with the study partner:
 - Visit registry, concomitant meds, NPI, Stereotypic/Ritualistic behaviors, Zarit Burden Interview, study drug issue/return log

Post-visit:

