- □ If no contradictions per study clinician, instruct participant/study partner to increase dose to 450mg/day (one pill mornings, two pills evenings), using two new bottles.
- □ Schedule Week 6 visit with participant for 2 weeks after their week 2 visit.
- Obtain clinician signature on REDCap study drug issue/return log resolve any missing data from clinician forms

Week 6

Pre-visit:

Schedule an at-home blood draw via ExamOne, to occur as close to the virtual visit as possible. Notify the CALM lab of the anticipated date of this visit so they can expect the shipment. Remind study partner not to give medication dose morning of blood draw.

- □ Create zoom link & send along with date/time of visit & visit schedule to the study partner
- □ Send a calendar invitation to the study physician. In the calendar invitation, include:
 - o Zoom link
 - Links to clinician forms within REDCap for the correct subject/week
 - List of clinician forms: Treatment emergent symptoms, CGI-Severity, CGI-Change
 - Current subject medication dose, anticipated dose change after visit, & any other relevant information

During visit:

- □ Complete medication compliance check: have study partner count pills remaining in the bottle they have been using. Each bottle contains 28 pills, so calculate the number of pills that should be remaining based on dose & time since the last visit.
- On REDCap, complete the following forms with the study partner:
 - Visit registry, concomitant meds, NPI, Stereotypic/Ritualistic behaviors, study drug issue/return log

Post-visit:

- Following the at-home blood draw, complete a Serum Sham Lithium Level Form (dopamine>Lithium in FTD>Serum-Sham Lithium Levels) and send it to [name], who will send the form to [name] along with the REAL serum lithium level (once it is available on CALM). [name] will then complete the form and send it back to [name], who will send it to you. Save the signed form in a unique subject folder in dopamine>Lithium in FTD>Serum-Sham Lithium Levels.
- If no contradictions per study clinician, AND serum lithium/sham level is within the target window, instruct participant/study partner to increase dose to 600mg/day (two pills mornings, two pills evenings), using two new bottles.
- Obtain clinician signature on REDCap study drug issue/return log, resolve any missing data from clinician forms, fill out serum-sham lithium level REDCap form.

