- Following the at-home blood draw, complete a Serum Sham Lithium Level Form (dopamine>Lithium in FTD>Serum-Sham Lithium Levels) and send it to [name], who will send the form to [name] along with the REAL serum lithium level (once it is available on CALM). [name] will then complete the form and send it back to [name], who will send it to you. Save the signed form in a unique subject folder in dopamine>Lithium in FTD>Serum-Sham Lithium Levels.
- If no contradictions per study clinician, AND serum lithium/sham level is within the target window, instruct participant/study partner to stay at OR increase dose to 600mg/day (two pills mornings, two pills evenings), using two new bottles.
- □ Obtain clinician signature on REDCap study drug issue/return log, resolve any missing data from clinician forms, fill out serum-sham lithium level REDCap form.
- □ Schedule Week 10 visit with participant for 2 weeks after their week 2 visit.
- □ If not already done, schedule in-person week 12 visit and submit room request to Irving

Week 10

Note: there is no blood draw associated with this visit unless the medication dose was increased at week 8. If this is the case, follow instructions related to at-home blood draws & serum/sham lithium levels.

Pre-visit:

- □ Create zoom link & send along with date/time of visit & visit schedule to the study partner
- □ Send a calendar invitation to the study physician. In the calendar invitation, include:
 - o Zoom link
 - o Links to clinician forms within REDCap for the correct subject/week
 - o List of clinician forms: Treatment emergent symptoms, CGI-Severity, CGI-Change
 - o Current subject medication dose & any other relevant information

During visit:

- □ Complete medication compliance check: have study partner count pills remaining in the bottle they have been using. Each bottle contains 28 pills, so calculate the number of pills that should be remaining based on dose & time since the last visit.
- On REDCap, complete the following forms with the study partner:
 - Visit registry, concomitant meds, NPI, Stereotypic/Ritualistic behaviors, study drug issue/return log

Post-visit:

- □ Instruct participant/study partner to stay at current dose, using two new bottles.
- Obtain clinician signature on REDCap study drug issue/return log, resolve any missing data from clinician forms.

Week 12

Pre-visit:

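### The visit checklists default to a dose increase with no test of clinical need, although the titration rule in the Introduction requires one

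*Combined protocol and SAP*

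**What the plan says.** The governing rule is in the Introduction: "This upward dose titration will occur if clinically indicated, tolerated by the patient, and based on real/sham lithium blood level". The next sentence defines the first condition: "An absence of response at lower doses without intolerable side effects is defined as clinically indicated". The Introduction also ranks the evidence, stating that clinical response and side effects "will override the information obtained from serum lithium levels if such a choice needs to be made".

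The visit sections agree with this. The Week 2 Visit and Week 4 Visit sections allow an adjustment based on clinical response and side effects. The Week 6 Visit and Week 8 Visit sections allow up to 600 mg/day where it is needed, based on clinical response, side effects and the blinded level. The section on blinding and lithium/sham levels has the study physician adjust the pills on level, clinical response and tolerability.

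The post-visit lines under Visit Checklists read differently:

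- Week 2: "If no contradictions per study clinician, instruct participant/study partner to increase dose to 300mg/day".
- Week 4: "If no contradictions per study clinician, instruct participant/study partner to increase dose to 450mg/day".
- Week 6: "If no contradictions per study clinician, AND serum lithium/sham level is within the target window, instruct participant/study partner to increase dose to 600mg/day".
- Week 8 has the same opening condition, then: "AND serum lithium/sham level is within the target window, instruct participant/study partner to stay at OR increase dose to 600mg/day".
- Week 10 tells staff to keep the current dose, with no exception.

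**The concern.** The two texts start from opposite defaults. The Introduction asks whether there is a reason to raise the dose. The checklists ask whether there is a reason not to. At weeks 6 and 8 the checklists also make an in-window level a condition of the instruction, whereas the Introduction treats the level as one input that response and side effects can override.

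The checklists are what a coordinator has in hand around a visit and when telling the caregiver what to give. If they are followed literally, a patient who is already doing well can be moved to a higher lithium dose for no stated reason. A patient who is not responding and has room to go up can miss the prompt for the last step. At stake are unneeded exposure in the first case, under-titration in the second, and dosing that may vary with the text that guides the instruction.

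**Working it through.** The plan gives no figure to reproduce here, so the check is a comparison of texts followed by two test patients.

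**Side by side**

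| Visit | Body text: basis for the step | Checklist: conditions for the step | Need tested in checklist? |
|---|---|---|---|
| Week 2 (to 300 mg/day) | Response, side effects | No contradictions | No |
| Week 4 (to 450 mg/day) | Response, side effects | No contradictions | No |
| Week 6 (to 600 mg/day) | Need, on response, side effects, level | No contradictions and level in window | No |
| Week 8 (to 600 mg/day) | Need, on response, side effects, level | No contradictions and level in window | No |

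Step-up lines without a need test: 4 of 4. Lines that also fall silent when the level is below the window: 2 of 4 (weeks 6 and 8).

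The Week 8 line is ambiguous. The four-pill schedule in its parenthesis suggests that the patient ends at 600 mg/day either way. It could also be read as allowing the current dose to stand. Neither reading contains a need test.

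**Test patient 1: week 6, 450 mg/day, has responded, no side effects, level in window.** Introduction: absence of response is not met, so no increase is indicated. Checklist: both conditions are met, so the instruction is 600 mg/day. The texts conflict. The same conflict arises for a tolerating responder at weeks 2 and 4, where no level condition applies.

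**Test patient 2: week 6, 450 mg/day, no response, no side effects, level below the window.** Introduction: an increase is clinically indicated, and response outranks the level. Checklist: the level condition fails, so the line says nothing.

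**Does an in-window level stand in for need?** No. It carries no information about response. Nor does it establish that there is room to go up. If the level is assumed proportional to dose (an illustration; the documents do not say so), the step multiplies it by 600/450 = 1.33. A level above 0.6 × 450/600 = 0.45 mmol/L on 450 mg/day would then project above the 0.6 upper limit.

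**Which window?** The Introduction says "Optimal target serum levels of lithium will be between 0.2 to 0.6 mmol/L"; the blinding section puts the lower bound at 0.4. The checklists do not say which applies. Test patient 2 covers a further 0.4 − 0.2 = 0.2 mmol/L of levels under the higher bound. That discrepancy is a separate matter and is not settled here.

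**Duration.** Time at 600 mg/day by week 12 is at most 12 − 6 = 6 weeks after a week-6 step, 12 − 8 = 4 after a week-8 step, and 12 − 10 = 2 after a week-10 adjustment. These are upper limits, because the sample must be shipped and the level form must pass through the unblinded staff before the dose is decided.

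**Week 10.** The Week 10 Visit section provides for adjustments that are still needed, within the 600 mg/day cap. The Week 10 checklist line does not reflect this.

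**The case against.** The best defence is that the checklists are abbreviations. They are offered for reference and send the reader back to the earlier sections. Each step-up line defers to the study clinician, who at these same visits rates CGI severity, CGI change and treatment-emergent symptoms, and so has response and tolerability in view. Under the blinding section the physician chooses the dose and the coordinator passes it on. Sham levels put both arms through the same lines.

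Most of this stands, and it is why the point is minor. It does not remove the conflict. A clinician who finds no contradiction has not thereby found a need, and a pointer to further detail does not reconcile two different rules. The checklists also have the coordinator send the physician the expected dose change before each of these visits, which reinforces the upward default. Where the blinding section describes the physician's decision once the level form is back, it lists level, dose, interval, tolerability and side effects but not clinical response, so that step does not clearly restore the missing test.

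A reader might infer that the Week 6 and Week 8 lines forbid an increase when the level is low. They do not: they are silent, and the Introduction and blinding section still cover that patient.

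A reader might also infer that all 60 planned patients (30 per arm) are dosed under these lines. The documents do not support that. The checklists describe the hybrid-remote visits introduced during COVID, in a manual dated 31 May 2021. The documents do not say how many patients came before that or what lines applied to them. The Power Analysis also allows for 20% attrition, so some patients may never reach weeks 6 and 8.

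**Conclusion.** Wrong as written, and minor. All four step-up lines omit the clinical-need condition that the Introduction imposes. Read literally, they escalate a tolerating responder (with an in-window level at weeks 6 and 8), and at weeks 6 and 8 they leave a tolerating non-responder below the window without a prompt.

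This rests on a literal reading of the checklist lines. The physician's decision, the reference back to the body text and the 600 mg/day cap limit the harm. The number of patients affected is unknown. No endpoint, analysis or sample-size figure changes.

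It would go too far to conclude that a patient who never reaches 600 mg/day was failed by the checklist: the physician may properly decide against that dose. Nor do the documents show that the wording biases the comparison between arms.

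**What to change.** Reword the Week 2, 4, 6 and 8 post-visit lines along these lines:

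> If the study physician decides an increase is clinically indicated (no response and no intolerable side effects at the current dose; see Introduction), after reviewing the real/sham level at weeks 6 and 8, instruct the increase to [300/450/600] mg/day; otherwise follow the study physician's decision to continue, hold or reduce the dose. A level below the target window does not by itself prevent an increase; a level above 0.6 mmol/L is by default a reason not to increase.

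The alternative to an increase has to include holding or reducing the dose, so that a patient with intolerable side effects and a level at or below 0.6 mmol/L is not told to carry on. The wording uses only the 0.6 upper bound, which both stated windows share.

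In the Week 10 post-visit line, add that the current dose continues unless the study physician adjusts it, to match the Week 10 Visit section.

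Cost: four reworded lines and one added phrase, with IRB review of the revised manual if the site requires it. No extra visits, blood draws, patients or analyses.
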